#### **8.4 HIV Risk Assessment**

**8.4.1 Sexual and Sexual Risk Behavior Assessment:** The SERBAS (Sexual Experiences and Risk Behavior Assessment Schedule)(Meyer-Bahlburg et al., 1991; Sohler et al., 2000), a psychometrically sound, longstanding, extensively used instrument of the Columbia University HIV Center For Clinical and Behavioral Studies will be the source of our primary outcome measure, number of unprotected (vaginal and anal) penetrative intercourse occasions, as well as other secondary sexual and sexual risk behavior outcomes for the time period of the past 3 months. SERBAS items will include: 1) number of unprotected penetrative intercourse occasions and number of unprotected penetrative intercourse occasions by (main versus casual) partner type; 2) number of partners, gender of partners, HIV serostatus and HIV risk characteristics of partners; and 3) pursuit of HIV testing and counseling. The SADAR (Sex and drug abuse relationship interview) (Calsyn et al., 2000) will be the source of the secondary outcome measure, proportion of drug or alcohol with sex occasions of all sex occasions; and proportion of unprotected occasions of all sex occasions. It should be noted that the use of these items will permit the comparison of results from the women's and men's studies. All items will be administered using the ACASI method. SERBAS items are currently being used in ACASI format in a 1200-person NIMH multi-site intervention study with HIV seropositive IDUs, female sexual partners of IDUs, and men who have sex with men.

We acknowledge the potential for compromised recall posed by our primary outcome assessment of number of unprotected penetrative intercourse occasions during the past 3 months. We acknowledge that this is particularly true if alcohol and drugs are used before sex. However, we maintain that there are compelling precedents for using this outcome and time frame in HIV risk behavior intervention studies with comparable populations. These include: (1) samples of men and women in community-based STD or health clinics in 5 urban areas--including substantial proportions of drug-users (NIMH Multi-site HIV Prevention Trial Group, 1998; Pinkerton et al., 2002); and (2) a sample of

women in an inner-city family planning clinic--including a substantial proportion of women with recent drug use (Ehrhardt et al., 2002). We also maintain that there is considerable quantitative evidence of the reliability and validity of both the SERBAS (Sexual Experiences and Risk Behavior Assessment) (for example, MacKinnon et al., 1993; Meyer-Bahlburg et al., 1997; Sohler et al., 2000; Ehrhardt et al., 2002) and RBS (Risk Behavior Survey) (for example, Simpson et al., 1994) instruments—that are the basis of our proposed study assessment. We offer a more explicit description of administration procedures to demonstrate the feasibility of the time frame. In particular, we clarify that, in quantifying occasions of (general and unprotected) sexual behavior during the past 3 months, the participant is advised about strategies to improve recall. These include: using smaller units of time (i.e. a week) to construct the past 3 months; identifying critical events during this period, relative to which she might more readily recall her behavior; identifying atypical times during this period, when her behavior digressed dramatically from her usual behavior over this period and others.

#### **8.4.2 Perceived self-efficacy to carry out safer sex**

Following [name] and colleagues, the Condom Use Self-Efficacy Scale (Marin, Tschann, Gomez and Gregorich, 1998) will be used to measure a participant's belief in her ability to protect herself during sex and to negotiate safer sex. This 11 (5 point Likert) item scale has been used with 1600 unmarried Latino adults in 10 U.S. states. Perceived self-efficacy is the sum of the 11 items (range: 0-44). Factor analyses revealed 5 correlated factors: regular partner, impulse control, partner resistance, STD ideas, and condom discussion. Preliminary psychometrics indicate good reliability (Cronbach's alpha = .86) and good concurrent validity.

#### **8.4.3 Perceived barriers to safer sex**

The Condom Barriers Scale (ST. Lawrence, Chapdelaine, Devieux et al., 1999), will be used to assess 4 domains of reluctance to use male condoms. This is a 29 (5 point Likert) item scale, with demonstrated reliability and validity, from which a total score is obtained. Domains include: access/availability; partner barriers; effect on sexual experience; and motivational barriers. The Attitude Toward The Female Condom Scale will be used to assess reluctance to use female condoms.

#### **8.4.4 Condom use skill behavior assessment**

Condom use skill is measured, separately, for male and female condoms using checklists of necessary actions. It is measured by (dichotomous) observer ratings of the presence or absence of basic skills for use of each. For each, a total count of number of skills observed is obtained. The following skills for putting a male condom on a penis model are observed: Expiration date on package is checked; package is opened carefully; condom checked for damage; condom rolled correctly downward; condom rolled to base of penis; air removed from condom; space left at tip of condom; lubricant added to condom or penis; withdrew condom and moved away from mode; took care to avoid spilling; and tied off condom and disposed of in trash. The following skills for putting a female condom in a vagina model are observed: expiration date checked; the package is opened carefully; condom checked for damage; condom unrolled and two rings separated; condom rubbed gently to evenly spread lubricant; inner ring squeezed between finger; inner ring pushed into vaginal canal while squeezed; inner ring placed against cervix; outer ring covers outside of vagina; after used condom is twisted and removed taking care not spill contents; and condom disposed of in trash can.

#### **8.4.5 Negotiation skill behavior assessment**

Negotiation skill is measured by (4-point Likert scale) assessor ratings of the extent of 4 basic negotiation skills demonstrated in participants' completion of sexual risk vignettes. These skills are: assertiveness (in demanding safer sex from partners); informativeness (about the need for safer sex); ability to anticipate high-risk situations (demonstrated by mention of carrying condoms); and implementation (of safer sex skills). A total skill score can be obtained by summing these. A count of number of alternative solutions is generated. A count of number of obstacles identified is generated.

#### **8.4.6 Bem Sex Role Inventory**

The Bem Sex Role Inventory-Short Form (BSRI) (Bem, 1981) will be used to assess degree of masculine and/or feminine gender role attitude. One focus of the SSB intervention is to empower women to adopt more active, less stereotypically feminine gender role behavior in their sexual relationships. It consists of 11 7-point Likert scale items – on which the subject can be categorized as masculine, feminine, or gender-neutral. Mean scores ranging from 1 - 7 for feminine, masculine, and neutral gender role items, are obtained from the mean ratings for each category. In order to reduce respondent burden, 'filler' items, which do not load on to either the femininity or masculinity scales, were eliminated in the short form (Bem, 1981).

#### **8.4.7 Past and current abuse experience assessment**

This assessment includes physical, sexual and emotional abuse items. In each domain the participant is asked to report: lifetime occurrence (YES/NO); lifetime frequency (4-point scale from once to regularly); need for medical treatment (YES/NO); use of medical treatment (YES/NO); length of time since last occurrence; occurrence with main partner (YES/NO); occurrence with other than main partner (YES/NO); and past 3 month frequency (on a 1 – 6 scale of daily to no occurrence). Participants are also asked age of first sexual abuse and description of perpetrator (e.g. different family members, strangers, etc). It has been shown that abuse is positively associated with sexual risk behavior.

#### **8.4.8 Attitudes Toward Female Condoms**

This assessment measures participants' attitudes toward the use of the female condom. It consists of 18 items scored on a 5-point Likert scale (strongly disagree to strongly agree). Five additional questions ask about intent to use the female condom, with what kind of partner, and whether this will be in the next 3-month period of time.

#### **8.4.9 Gender Specific Questionnaire**

This measure contains questions related to contraception, pregnancy, and STDs that are not found elsewhere in the assessment battery. The participant is asked to provide a brief history of pregnancies she might have had, her use of contraception, and a history of STD prevalence. This measure will be administered at baseline and updated at the 3 and 6 month follow up point.

#### **8.4.10 Sexual Relationship Power Scale**

The Sexual Relationship Power Scale (SRPS) (Pulerwitz, Gortmaker, & DeJong, 2000) measures power dynamics in relationships using two subscales: Relationship Control and Decision-Making Dominance. The scale was shown to be inversely related to

physical violence and related to consistent condom use. It consists of 23 items scored on a 4-point Likert scale (strongly agree to strongly disagree). The measure will be administered at baseline, immediate post treatment, 3, and 6 month follow up points.

### **8.5 Adverse Event Evaluation**

An adverse event (AE) is defined as any reaction, side effect or untoward event that occurs during the course of the clinical trial. The possibility of abusive partner behavior and/or a marked increase in emotional distress (defined as an increase in depression and/or anxiety symptoms) are the foreseeable adverse effects of participation. Possible triggers for these effects could be: introduction of (male or female) condoms or other methods of protection; introduction of safer sex negotiation; refusal of unprotected sex; or partner knowledge of the woman's participation in a woman's intervention. Subjects are advised to observe any signs of anger in their partners, and any of these problems in themselves, and to discuss this with study staff immediately. Study staff will be trained to provide crisis intervention and referral for clinical emergency situations. In addition, all study assessments contain modules concerning abuse that can alert study staff to evolving risk. The occurrence of AEs will be determined through the use of an AE Worksheet (consisting of one general AE question and a follow up question to gather more information) filled out by the RA at baseline, immediate post treatment, 3 and 6 month follow up assessments. All SAEs will be recorded, respectively, on the AE Case Report Form (CRF) and SAE Form and SAE Summary Report. The procedures for detecting, reporting and monitoring SAEs are described in section 9.0.

### **8.6 Treatment Compliance**

Subjects will be asked to complete an intervention exposure checklist -- designed to measure whether the participant has been exposed to the interventions provided in both the intensive gender specific SSB intervention and the HE comparison condition. The participant checks the interventions she has been exposed to during the assessment period, and identifies the source of exposure. Therapists will be asked to complete an intervention fidelity questionnaire after each intervention session – to document the content and the activities of the sessions they conducted.

**9.0 DATA SAFETY AND MONITORING PLAN**

The data safety monitoring plan consists of three components: safety; trial performance; and efficacy. Procedures for monitoring and assuring these components will be

presented here, or references to other sections of the protocol where these procedures are detailed will be provided.

## **9.1 Safety**

### **9.1.1 Definition of Adverse and Serious Adverse Events**

Adverse events will be categorized as serious or non-serious, as related or not related to the study, and as expected or unexpected. An adverse event is defined as any reaction, side effect, or untoward event that occurs during the course of the clinical trial. Stable chronic conditions which do not worsen are not considered AEs. Clinically insignificant events will be excluded from any type of documentation. These may include: colds, flu, cuts, scrapes, coughs, headaches, stomach complaints, general fatigue and mild symptoms or problems associated with medical conditions not related to drug use.

A serious adverse event (SAE) is defined as: any fatal event; any immediately life-threatening event; any permanent or substantially disabling event; any event that requires initial hospitalization or prolongs hospitalization (excluding normal childbirth and pre-planned or elective procedures); any event causing congenital anomaly or birth defect; or any event requiring intervention to prevent any of these problems. Hospital visits that do not result in admittance are not considered SAEs (e.g. emergency room visit that does not result in admittance).

Risks from behavioral intervention trials may be expected to be minimal relative to those from pharmacologic interventions. The possibility of abusive partner behavior and/or a marked increase in emotional distress (defined as an increase in depression and/or anxiety symptoms) are the foreseeable adverse effects of participation.

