### **9.1.2 Assessment, Reporting and Monitoring of Adverse and Serious Adverse Events**

AEs and SAEs will be elicited by research assistants at each assessment (baseline through follow up). The RA will ask the subject whether she has experienced any new problems or a worsening of existing problems since her last assessment using the AE Worksheet. The RA should be focused on gathering data to aid the Study Clinician in determining study relatedness. Assessment of depression must include an assessment of suicidal ideation, as suicidal ideation may require immediate clinical assistance and qualify as an SAE. All clinically significant AEs will be captured on a standardized AE Log, with immediate assessment for whether or not the AE is serious, and whether or not the AE is study-related, in consultation with the site coordinator or Study Clinician (PhD, MD, PI). Study-relatedness will ultimately be determined by the Study Clinician following discussion with the staff member reporting the AE. AEs that are not serious or study related do not require any further paperwork documentation besides the AE Log. AEs and SAEs could also be spontaneously disclosed by the subject during intervention sessions. In this case, the therapist will record and report them, as described here.

Study staff will be trained to provide crisis intervention and referral for clinical emergency situations. Standard CTP procedures for handling crisis situations should be used. The Site Coordinator and/or Study Clinician will be available by beeper (or other similar method), within 24-hours for consultation and crisis intervention for problems.

From baseline informed consent discussion onward, subjects are advised that conversation about HIV or STDs, introduction of (male or female) condoms or other methods of protection, safer sex negotiation, refusal of unprotected sex, or, even their participation in a women's intervention may anger their male partners. This anger may put them at risk for emotional, physical and/or sexual abuse. Subjects are also advised that emotional distress could develop or increase in response to these problems. For this reason, subjects are advised to observe any signs of such anger in their partners, or such problems in themselves, and to discuss them with study staff immediately. In addition, study assessments contain modules concerning abuse, which can alert the study staff to evolving risk.

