### 11.7 Analysis of Safety Measures

For each individual adverse experience, each participant will be categorized by the maximal severity reported during the intervention phase. Adverse experiences occurring during screening but ending prior to randomization, or those starting during screening and continuing into the randomization phase with the same or less severity will be excluded. The severity categories are: none (if the participant never had the adverse experience), mild, moderate, severe, life threatening and lethal. If a participant has an adverse experience more than once, then the adverse effect with most severe rating will be used in the analysis. It may be necessary to group the individual adverse experiences before any analysis can be performed. If this is necessary, then the coding will be performed centrally by Long Island node personnel.

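### Section 9.1.1 lets minor injuries go undocumented with no exception for cause, so an injury inflicted by a partner can miss the AE Log and never be judged for study-relatedness

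*Protocol*

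**What the plan says.** Section 9.1.1 sets the rule and then gives examples: "Clinically insignificant events will be excluded from any type of documentation. These may include: colds, flu, cuts, scrapes, coughs, headaches, stomach complaints, general fatigue". The list ends with "mild symptoms or problems associated with medical conditions not related to drug use". The same section names two foreseeable adverse effects of taking part: abusive behavior by a partner, and a marked increase in emotional distress, which it glosses as "defined as an increase in depression and/or anxiety symptoms".

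Section 9.1.2 sets the next step: "All clinically significant AEs will be captured on a standardized AE Log". Seriousness and study-relatedness are assessed at that point, and the Study Clinician has the final word on relatedness. Only SAEs and related AEs then enter the study database, through the AE CRF.

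Events are elicited with an AE Worksheet which, according to section 8.5, has "one general AE question and a follow up question to gather more information". Table 2 schedules it at baseline and at all three later visits. Section 8.5 also says that every study assessment includes abuse modules. Table 2 shows the abuse assessment at baseline and, for current abuse only, at 3 and 6 months. It has no entry for it at Visit 2, the immediate post-intervention visit.

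Section 11.7 classifies each woman by maximal severity, with these categories: "none (if the participant never had the adverse experience), mild, moderate, severe, life threatening and lethal".

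**The concern.** The exclusion names kinds of complaint and is silent on cause. Cuts and scrapes are a plausible way for a minor assault to present. Section 9.1.2 itself warns participants that introducing condoms, negotiating or refusing unprotected sex, or simply joining a women's intervention may anger a partner and expose them to abuse, including physical abuse. The examples of what need not be written down therefore include signs of a harm that the trial expects it might cause.

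The order of the steps makes this matter. Clinical significance is decided first, and relatedness is assessed only for what passes. For a foreseeable harm of the intervention, cause is part of what makes an event significant, so it should be known before the event is set aside. At stake are the completeness of the AE Log for partner-inflicted injury, and the chance for the Study Clinician to judge such an injury as related.

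**Working it through.** No arithmetic in the plan bears on this, and the protocol gives no rates of partner violence or of minor injury. The check is a comparison of sections, plus one timing calculation.

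**Path of a minor injury through the AE process**

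1. The research assistant asks the general question and the follow-up question (8.5). Neither is described as asking about cause or about a partner.
2. The event is judged clinically significant or not (9.1.1). The section gives no definition, no named decision-maker and no exception for cause. If the event is judged insignificant, nothing is documented.
3. If it is judged significant, it goes on the AE Log, and seriousness and relatedness are assessed (9.1.2).
4. If it is serious or related, it enters the database (9.1.2).
5. Severity is tabulated (11.7).

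An event that stops at step 2 cannot be found related at step 3. Section 9.1.2 tells the research assistant to gather data bearing on relatedness, but for such an event 9.1.1 leaves no record to hold those data.

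**Whether the separate abuse assessment covers the gap**

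Section 8.4.7 describes it as covering physical, sexual and emotional abuse, with a past-3-month frequency item. It does not pass through the significance filter. It has two limits here.

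- *Visit 2.* Table 1 places this visit 21 days after the first session, and section 6.3 runs the SSB sessions over 3 weeks. Table 2 schedules no abuse assessment at this visit. The AE entry is the only item listed there that is directed at adverse events.
- *Recall at Visit 3.* Table 1 places this visit 15 weeks after the first session. Section 4.0 accepts data from 14 days before to 30 days after the scheduled date. Assuming that 3 months is about 13 weeks, the recall window opens as follows:

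| Visit 3 timing | Visit, weeks after first session | Window opens (visit − 13) |
|---|---|---|
| 14 days early | 15 − 2 = 13 | week 0 |
| On schedule | 15 | week 2 |
| 30 days late | 15 + 30/7 ≈ 19.3 | about week 6.3 |

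On schedule, the frequency item misses about the first 2 of the 3 session weeks. At the late limit it misses all 3. Only at the early limit does it reach back to the first session. For part of the intervention period, then, the AE process is the main scheduled route by which partner-inflicted injury would be recorded. As described, the abuse assessment also records no judgement of relatedness to the study.

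**The severity table in 11.7**

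Two rules act on it. Section 9.1.1 removes events judged insignificant, and section 9.1.2 keeps every non-serious event judged unrelated out of the database, whatever its severity. If the table is built from the database, a woman with an event lost by either route would be counted as never having had it. Neither rule is reconciled with a scale that runs from none through mild.

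**The case against.** The strongest reply is that 9.1.1 excludes events that are clinically insignificant, and that the complaints are only examples of what may fall under that heading. Not every cut is insignificant, and an injury known to come from a partner could well be judged significant, because abusive partner behavior is itself named as an adverse effect. Staff are also trained to recognise partner abuse and distress (9.1.3), all staff receive common AE training, therapists report events disclosed in sessions, and women are asked to report partner anger at once (9.1.2). All of this stands, and it makes the loss of a disclosed assault less likely. It does not supply the missing exception or name who decides, and about 12 sites could apply an undefined discretion differently.

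A reader might go further than the text allows in four ways.

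- *That mild distress or sexually transmitted symptoms are excluded by name.* They are not. The last class is limited to problems associated with medical conditions as well as to those unrelated to drug use. The foreseeable distress harm is a marked increase, even though the parenthesis defines it loosely. Distress is reached only indirectly, through complaints such as headache or fatigue.
- *That partner abuse is under-counted in the trial data.* The abuse assessment at baseline, 3 and 6 months does not depend on the AE filter. The exposed parts are the AE record and the relatedness judgement.
- *That 9.1.1 alone empties the mild category in 11.7.* The database rule in 9.1.2 contributes at least as much.
- *That Visit 2 certainly has no abuse questions.* Table 2 shows none, while 8.5 says that all assessments have them. The documents conflict, and that conflict is the finding.

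**Conclusion.** The point holds for injuries. As written, sections 9.1.1 and 9.1.2 allow a minor injury inflicted by a partner to be left undocumented before its cause is considered, so that it never receives a relatedness judgement. The frequency of this cannot be estimated from the protocol. What can be said is structural: an event set aside at the significance step cannot reach the AE Log, the AE CRF or the 11.7 table.

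The conclusion rests on reading 9.1.1 and 9.1.2 as sequential, which is how they are written, and on taking Table 2 as the operative schedule for Visit 2. If abuse modules are in fact given at that visit, as 8.5 states, the gap narrows, but the missing exception for cause remains. This should be corrected as a specific and inexpensive improvement in safety recording. It does not undermine the efficacy analysis or the trial's own measurement of abuse.

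**What to change.** 1. Add to 9.1.1 that the cause must be asked before an event is called clinically insignificant. Any injury inflicted by another person, and any event the participant links to partner anger, safer-sex negotiation or study participation, goes on the AE Log at any severity for the Study Clinician's relatedness judgement. Carry the same instruction into the AE Worksheet guidance.
2. State in 9.1.1 who judges clinical significance.
3. Reconcile 8.5 with Table 2 on whether abuse is assessed at Visit 2.
4. Reconcile 9.1.1 and the database rule in 9.1.2 with 11.7, so that the none and mild categories describe what will actually be recorded. The first change alone does not achieve this, because logged events that are non-serious and judged unrelated still do not enter the database.

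The cost is a few sentences of text and some additional minor AE Log entries. The first two changes need no new visit, staff or instrument. The third needs either a corrected sentence or an added entry in the schedule, depending on which statement was intended.
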